## 4.2 MEDICAL HISTORY

Medical history will be coded with the Medical Dictionary for Regulatory Activities (MedDRA) Terminology. Events will be coded to System Organ Class (SOC) and preferred term (PT) using MedDRA Version 22.0 or higher. The number and percent of subjects with clinically significant medical history at screening will be summarized by SOC and PT by treatment group and overall for the ITT and Safety Populations. Documented history of an inadequate response after at least 8 weeks of prior oral iron therapy use will be included in medical history.

## 5. STUDY DRUG

### 5.1 TREATMENT COMPLIANCE

As for each subject, the individual compliance rate will be summarized by descriptive statistics for ITT population.

FCM Compliance = (total dose of iron administered/target dose) × 100

Oral iron compliance = (total dose of iron taken/total dose prescribed) × 100

### 5.2 PRIOR AND CONCOMITANT MEDICATION

Prior medications are defined as medications that started prior to the first dose of study drug. Concomitant medications are defined as medications (other than the study drug) taken on or after the first dose of the study drug during the entire study. Medications started before the first dose of study drug and continuing at the time of the first dose of study drug are considered both prior medication and concomitant medication. As for the medications that stopped with end date prior to study drug start date will be considered as prior medications. Partial dates for prior/concomitant medication will be classified based on rules in Section 2.3.4.

All investigator terms for medications recorded on the CRF will be coded using the World Health Organization (WHO) Anatomical Therapeutic Chemical (ATC) drug dictionary (WHODrug, March 2019 B3). Summaries of prior and concomitant medications will be provided by level 3 ATC classification and preferred term using frequency and percentages by treatment

group and overall for safety population. If ATC level 3 is not applicable, then the level 2 ATC will be used.

## 6. EFFICACY ANALYSES

All efficacy analyses will be based on the ITT Population. Missing data will be imputed per Section 2.3.4 for statistical inference analysis (no imputation for descriptive statistical summaries).

### 6.1 PRIMARY EFFICACY ANALYSIS

#### 6.1.1 Change in hemoglobin from baseline to Day 35

The actual value of hemoglobin on baseline, Day 35, and change from baseline to Day 35 will be summarized via descriptive statistics by treatment group.

Treatment group difference for change in hemoglobin will be assessed with the analysis of covariance (ANCOVA), with treatment and randomization strata (hemoglobin and age categories) as fixed factors and baseline value of hemoglobin as a covariate. Baseline hemoglobin will be defined as the last hemoglobin obtained before randomization. Missing value will be imputed using LOCF as specified in Section 2.3.4. P-values to test treatment effect will be determined. Point estimates, associated 95% confidence interval and p-values will be reported.

#### Supportive analysis

To assess the robustness of this primary efficacy analysis, supportive analyses will be performed using the MMRM model described in the following for this primary endpoint:

#### **MMRM Analysis of Change in hemoglobin from baseline to Day 35:**

A mixed model repeated measures (MMRM) model will be conducted to provide an analysis under the assumption that data are missing at random (MAR). The MMRM model will include changes in hemoglobin from baseline to each post-baseline visit as the dependent variables; and treatment group, visit and treatment group by visit interaction as fixed effects; and subjects within treatment group as random effects; and baseline hemoglobin (<10, ≥10 g/dL) and age (1 to <12 and ≥12 to 17 years) as covariate. An unstructured covariance matrix will be used to allow for unequal variances between visits. If the model does not converge with unstructured variance – covariance matrix, then the Toeplitz, first-order autoregressive, compound symmetric, variance components structures will be tried and the covariance structure will be decided based on model convergence status and the AKaike information criterion. The Kenward-Roger approximation will be used to calculate the denominator of degrees of freedom for the fixed effect. If the interaction term is not significant, it will be dropped from the model. No imputation of missing data other than that inherent in the MMRM model will be performed. P-values to test treatment effect on Day 35 will be reported. Point estimates and associated 95% confidence interval will be reported.

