**Sample Size Rationale:**

A total of 60 participants (30 per treatment group) are required to detect an expected difference in Hgb of 1.0 g/dL (common standard deviation = 1.16 g/dL) at two-sided alpha = 0.05 with 90% power.

Assuming 20% attrition of subjects not meeting the definition of modified intention to treat (mITT), approximately 72 participants will be randomized.

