### **8.6 Sample Size Rationale**

A total of 60 participants (30 per treatment group) are required to detect an expected difference in hemoglobin of 1.0 g/dL (common standard deviation = 1.16 g/dL) at two-sided  $\alpha=0.05$  with 90% power. Assuming 20% attrition of subjects not meeting the definition of mITT, approximately 72 participants will be randomized.

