### 1.3.2 Stratification/Randomization

On Day 0, participants who meet the inclusion/exclusion criteria will be randomized via IRT system in a 1:1 ratio to receive either FCM in Group A or oral iron (oral solution drops, elixir or oral tablets) in Group B. Randomization will be stratified by baseline hemoglobin (<10, ≥10 g/dL) and age (1 to <12 and ≥12 to 17 years).

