### 1.3.4 Sample Size and Statistical Power Considerations

A total of 60 participants (30 per treatment group) are required to detect an expected difference in hemoglobin of 1.0 g/dL (common standard deviation = 1.16 g/dL) at two-sided  $\alpha=0.05$  with 90% power. Assuming attrition of subjects not being evaluable for efficacy analysis, approximately 72 participants will be randomized.

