#### **MMRM Analysis of Change in ferritin from baseline to Day 35:**

A mixed model repeated measures (MMRM) model will be conducted to provide an analysis under the assumption that data are missing at random (MAR). The MMRM model will include changes in ferritin from baseline to each post-baseline visit as the dependent variables; and treatment group, visit and treatment group by visit interaction as fixed effects; and subjects within treatment group as random effects; and baseline ferritin and randomization strata (hemoglobin and age categories) as covariate. An unstructured covariance matrix will be used to allow for unequal variances between visits. If the model does not converge with unstructured variance – covariance matrix, then the Toeplitz, first-order autoregressive, compound symmetric,

variance components structures will be tried and the covariance structure will be decided based on model convergence status and the AKaike information criterion. The Kenward-Roger approximation will be used to calculate the denominator of degrees of freedom for the fixed effect. If the interaction term is not significant, it will be dropped from the model. No imputation of missing data other than that inherent in the MMRM model will be performed. P-values to test treatment effect on Day 35 will be reported. Point estimates and associated 95% confidence interval will be reported.

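### The hemoglobin MMRM adjusts for baseline hemoglobin only as <10/≥10 g/dL, unlike the primary ANCOVA and the other three MMRMs; adding the continuous value would align it at no cost (minor).

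*SAP*

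**What the plan says.** - **Primary analysis (SAP 6.1.1).** An ANCOVA of change in hemoglobin at Day 35 with LOCF. Treatment and the hemoglobin and age strata are fixed factors, with "baseline value of hemoglobin as a covariate". Protocol 8.4.1 specifies the same terms.
- **Hemoglobin MMRM (SAP 6.1.1, supportive analysis).** Its baseline terms are "baseline hemoglobin (<10, ≥10 g/dL) and age (1 to <12 and ≥12 to 17 years) as covariate". Both are categories; continuous hemoglobin does not appear.
- **Ferritin MMRM (SAP 6.2.1).** It uses "baseline ferritin and randomization strata (hemoglobin and age categories) as covariate". The TSAT (6.2.2) and reticulocyte hemoglobin content (6.2.6) models have the same form, each with its own baseline value.
- **Other checks on the primary result.** SAP 2.3.4 says that an observed-case version of the primary analysis will also be run. SAP 2.2.2 allows post hoc sensitivity analyses in the mITT population.
- **Changes from protocol (SAP 9).** Item 3 records that MMRM analyses were added. It does not mention or explain the different covariate set for hemoglobin.

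**The concern.** Of the four MMRMs, the one attached to the primary endpoint is the only one without the baseline value of its own outcome. Its wording echoes the stratification sentence in SAP 1.3.2, so a drafting slip is a plausible explanation, although the SAP does not say so.

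Three things are at stake, all within the supportive analysis:

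1. **Comparability.** The MMRM is there to show whether the LOCF ANCOVA result is robust to missing data. If the two models also adjust for different baseline terms, part of any gap between them may come from the adjustment. This holds whatever the slope of change on baseline.
2. **Missing at random.** That assumption is conditional on what the model contains. With only a two-level category, missingness related to baseline hemoglobin within a category is accounted for less fully.
3. **Precision.** If baseline predicts change within a category, the category-only model leaves that variation in the residual and does not correct chance imbalance inside a category.

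**Working it through.** **The plan's own figure.** SAP 1.3.4 states: "A total of 60 participants (30 per treatment group) are required to detect an expected difference in hemoglobin of 1.0 g/dL", with "common standard deviation = 1.16 g/dL"; the protocol synopsis gives "two-sided alpha = 0.05 with 90% power". The normal approximation is n per arm = 2 × 1.16² × (1.960 + 1.282)² / 1.0² = 28.3, so 29. The t-test has 89.7% power at 29 per arm and 90.7% at 30. The stated 30 per arm reproduces.

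**Inputs for the precision check**
- Baseline hemoglobin, mean (SD), and SD of Day 35 change, from Protocol Table 1: Cohort 1, 9.2 (1.20) and 1.38; Cohort 2, 9.5 (0.81) and 1.15.
- Upper limit of 11 g/dL, from inclusion criterion 2. Day 0 blood is drawn after treatment assignment (Protocol 6.3.1), so the last value before randomization is the screening value and the limit applies to baseline.
- Category cut at 10 g/dL, from the stratification.
- Slope β of change on baseline: **not in the documents**. Assumed range -0.3 to -0.7, with zero as the no-effect case.
- Further assumptions: baseline is normal and truncated at 11, and the relation to change is linear. The calculation is at Day 35 only and ignores the repeated-measures structure.

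**Formulas.** Let V be the variance of truncated baseline, W its average variance within the two categories, and σ the SD of change.
- Share of baseline variance captured by the category: 1 − W/V.
- Residual variance with continuous baseline: σ² − β²V.
- Residual variance with category only: σ² − β²V + β²W.
- SE ratio: the square root of the second residual variance divided by the first.

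**Share captured**
- Cohort 1 values: V = 1.1125, W = 0.6298, so 1 − 0.6298/1.1125 = 0.43.
- Cohort 2 values: V = 0.5623, W = 0.2746, so 1 − 0.2746/0.5623 = 0.51.

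**SE ratio, category only versus continuous baseline**

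| Slope β | Cohort 1 SDs (1.20 / 1.38) | Cohort 2 SDs (0.81 / 1.15) |
|---|---|---|
| 0 | 1.000 | 1.000 |
| -0.3 | 1.016 | 1.010 |
| -0.5 | 1.047 | 1.029 |
| -0.7 | 1.108 | 1.062 |

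Worked example for the largest entry: 1.38² − 0.49 × 1.1125 = 1.9044 − 0.5451 = 1.3593. Adding 0.49 × 0.6298 = 0.3086 gives 1.6679. √(1.6679/1.3593) = 1.108.

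**Cross-check on the correlation scale**, with σ = 1.16 and correlation ρ. The SE ratio is 1.02–1.03 at ρ = -0.3, 1.08–1.09 at -0.5 and 1.21–1.24 at -0.7. The slopes in the table correspond to correlations of about -0.20 (0.3 × 0.750/1.15) to -0.54 (0.7 × 1.055/1.38). A correlation of -0.7 with the Cohort 2 baseline spread would need a slope of about -0.7 × 1.16/0.75 = -1.08, so children with higher baseline would end lower; that end of the range is remote.

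**Power of the category-only model** at 30 per arm for 1.0 g/dL is 0.907 at ρ = 0, 0.92 at -0.3, about 0.94 at -0.5 and 0.96–0.97 at -0.7. It stays above 90% throughout. With continuous baseline the figures are 0.907, 0.93, 0.966 and 0.996.

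**The case against.** The strongest reply is that the omission touches one supportive model and nothing that decides the trial. The primary ANCOVA keeps continuous baseline hemoglobin, no success rule depends on the MMRM, and the stated sample size is unchanged. The MMRM was added in the SAP, so it contradicts no protocol model, and it contains the strata terms that Protocol 8.0 requires. All of this stands.

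Four stronger readings are tempting, and the documents do not support them:

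- **That the MMRM is the only model-based check on the primary result.** It is the only supportive model specified in SAP 6.1.1, but SAP 2.3.4 also plans an observed-case version of the primary analysis. Read naturally, that is the same ANCOVA without imputation, so it holds the covariates fixed and changes only the missing-data handling. It does not replace the MMRM: it gets one sentence with no model stated, and an observed-case ANCOVA would not use the Day 7 to Day 28 data of a child missing Day 35.
- **That dropout related to baseline is not handled.** A likelihood-based MMRM also conditions on the changes observed at earlier visits. If baseline predicts change, those changes carry part of the baseline information. The handling is weaker, not absent. A child with no post-baseline value contributes nothing in either version.
- **That the standard error could be 18% larger.** That figure pairs Cohort 1's baseline SD of 1.20 with the planning SD of 1.16 at slope -0.7. Table 1 gives that cohort a change SD of 1.38, and with the paired values the increase is about 11%.
- **That adding the covariate would isolate the missing-data effect.** The MMRM would still use all visits, may fall back on a covariance structure chosen by AIC, and drops the treatment-by-visit term if it is not significant. The LOCF side also uses a worst-value rule when the first post-baseline value is missing. The change removes one avoidable difference, not all of them.

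**Conclusion.** The inconsistency is a matter of text and is certain: the hemoglobin MMRM omits the continuous baseline value that the primary ANCOVA includes and that the three other MMRMs include for their own outcomes. No reason is given.

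The resulting covariate mismatch with the primary model, and the thinner conditioning for missing at random, follow from the model specification alone. The loss of precision does not. It depends on a slope that the documents do not give, on normal truncated baseline values, and on Phase II SDs carrying over to this trial. Under those assumptions it is about 1% to 11% in the Day 35 standard error, and it is zero if baseline is unrelated to change within a category.

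A reader might infer that the primary result or the power of the trial is compromised. It is not: the primary model and sample size are untouched, and the category-only model itself keeps more than 90% power for 1.0 g/dL over the correlations tried. Severity is minor. It is worth correcting because the correction costs almost nothing.

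**What to change.** In SAP 6.1.1, replace the baseline terms of the hemoglobin MMRM with: *baseline hemoglobin (continuous) and randomization strata (hemoglobin and age categories)*. This matches the covariates of the primary ANCOVA and the form of the ferritin, TSAT and reticulocyte hemoglobin content MMRMs.

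A baseline-by-visit term is optional. It is not needed for alignment, since none of the other three MMRMs has one and the ANCOVA has a single time point.

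The cost is one line of SAP text and one term in the model code. The primary analysis already uses the same baseline value, so no new data are needed. The change should be made before database lock.

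### The four supportive MMRMs pair a redundant random subject effect with an unstructured matrix, and every named fallback structure assumes equal variance at all visits, so a fallback can give a wrong Day 35 standard error in either direction

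*SAP*

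**What the plan says.** SAP 6.1.1 describes the hemoglobin MMRM, and 6.2.1 (ferritin), 6.2.2 (TSAT) and 6.2.6 (CHr) repeat its covariance wording. Five features matter here.

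- **Random effect.** The model includes "subjects within treatment group as random effects".
- **Residual matrix.** "An unstructured covariance matrix will be used to allow for unequal variances between visits".
- **Fallback.** If that fit does not converge, "then the Toeplitz, first-order autoregressive, compound symmetric, variance components structures will be tried". The choice among them rests on convergence and the Akaike criterion.
- **Inference.** Degrees of freedom are Kenward-Roger. No heterogeneous-variance structure, ante-dependence structure or sandwich standard error is named.
- **Interaction.** The treatment-by-visit term is removed if it is not significant, and the Day 35 treatment p-value is reported either way.

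The post-baseline visits are Days 7, 14, 28 and 35 (SAP 1.3.1), and the software is SAS 9.4 or higher (SAP 2.5). The MMRMs are supportive. Hemoglobin, ferritin and TSAT each have a Day 35 ANCOVA with LOCF as the main analysis, and SAP 2.3.4 adds an observed-case analysis for the primary endpoint. For CHr, SAP 6.2.6 gives only descriptive summaries and the MMRM.

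**The concern.** There are two linked defects.

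First, an unstructured matrix already describes every variance and covariance among the four visits. A random subject intercept adds a parameter that the data cannot distinguish from a shift in that matrix. A programmer who follows the text literally may get a singular Hessian or a convergence failure, which is exactly what triggers the fallback.

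Second, the fallback list abandons the property for which the unstructured matrix was chosen. All four structures carry a single variance across visits. AIC then compares only equal-variance candidates, so it cannot detect the problem, and Kenward-Roger does not correct a wrong covariance structure. Toeplitz and AR(1) indexed by visit order also treat the visits as equally spaced, although the gaps are 7, 14 and 7 days.

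At stake is the planned check that the LOCF-based primary result survives a missing-at-random analysis. A mis-sized Day 35 interval would make that check look more or less reassuring than it should. For CHr, the MMRM p-value is the only inferential result its section describes.

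**Working it through.** **Inputs from the documents.** SAP 1.3.4: "A total of 60 participants (30 per treatment group) are required to detect an expected difference in hemoglobin of 1.0 g/dL", with "common standard deviation = 1.16 g/dL". Protocol synopsis: "at two-sided alpha = 0.05 with 90% power". There are four post-baseline visits. No visit-specific SD is given; Table 1 in Protocol 3.2 reports screening and Day 35 only. Every early-visit SD below is therefore an assumption, with Day 35 held at 1.16.

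**Step 1: reproduce the plan's own figure.** n per arm = 2 × (1.96 + 1.2816)² × 1.16² / 1.0² = 2 × 10.51 × 1.3456 = 28.3, so 29 by the normal approximation. Power from the noncentral t is 89.7% at 29 and 90.7% at 30 per arm. The planned 30 per arm reproduces.

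**Step 2: identifiability.** Four visits give 4 variances and 6 covariances, which is 10 distinct quantities. The model has 10 unstructured parameters plus 1 random-intercept variance, which is 11. The Jacobian of the marginal covariance with respect to these has rank 10. In formula terms V = σ_b²J + R, where J is the matrix of ones, so any admissible σ_b² can be offset by R = V − σ_b²J. With assumed SDs of 0.6/0.8/1.05/1.16 and correlation 0.7 between adjacent visits, moving σ_b² from 0 to 0.15 keeps R positive definite and leaves V unchanged. The likelihood is flat in that direction. The fitted V, and with it the Day 35 estimate and model-based standard error, do not depend on the split.

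**Step 3: equal-variance fallback, interaction kept.** With complete data, a structure with one pooled variance gives approximately

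ratio = SE used / correct SE = √(mean visit variance) / 1.16, and type I error = 2 × [1 − Φ(1.96 × ratio)].

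A random intercept retained on top adds the same constant to every visit's variance, so the variances stay equal.

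| Assumed SDs, Days 7/14/28/35 | Mean variance | Ratio | Nominal 5% becomes |
|---|---|---|---|
| 0.5/0.8/1.1/1.16 | (0.25+0.64+1.21+1.3456)/4 = 0.861 | 0.80 | about 12% |
| 0.7/0.9/1.1/1.16 | (0.49+0.81+1.21+1.3456)/4 = 0.964 | 0.85 | about 10% |
| 0.9/1.0/1.1/1.16 | (0.81+1.00+1.21+1.3456)/4 = 1.091 | 0.90 | about 8% |
| 1.5/1.4/1.25/1.16 (falling) | (2.25+1.96+1.5625+1.3456)/4 = 1.780 | 1.15 | about 2% |

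A simulation at 36 per arm (8,000 runs) gave 11.8%, 9.9% and 7.7% for the three rising patterns with a pooled variance, against 5.1% with the visit's own variance.

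**Step 4: effect on the interval.** At 30 per arm the correct Day 35 half-width is 2.00 × 1.16 × √(2/30) = 0.60 g/dL. Multiplying by the ratio gives 0.48, 0.51 and 0.54 for the rising patterns and 0.69 for the falling one. In 20,000 simulated trials, pooled-variance coverage was 92.3% for 0.9/1.0/1.1/1.16, 95.0% for equal SDs and 97.7% for the falling pattern. With Day 35's own variance it was 94.7 to 95.3%.

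**Step 5: REML fits of the named structures.** These used 30 per arm, an assumed 10% dropout and 200 runs per pattern. Under a steep rise (0.4/0.6/1.0/1.16), all four structures gave a model standard error of 0.22 to 0.23 against an empirical 0.31, with coverage of 86 to 87%. Heterogeneous AR(1) gave 0.31 against 0.31, with 93.5% coverage. Under the falling pattern the four covered 98 to 99.5%. With 200 runs the Monte Carlo error at 86% coverage is √(0.86 × 0.14/200), about 2.5 points, so these runs confirm the direction more than the exact size.

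**Step 6: the SAP's interaction rule.** Steps 3 to 5 keep the interaction. Under the SAP's rule, with no effect at any visit, 36 per arm, complete data and correlation 0.8 per 7 days (1,000 runs), the interaction was dropped in over 90% of runs. Type I error under compound symmetry was then about 9%, 8% and 7% for the three rising patterns. Even the unstructured matrix gave 5.5 to 6.3% under the drop rule (20,000 runs).

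**The case against.** The best counter-argument is that this is a supportive model with a conditional defect. Much of that stands.

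- **The main analyses do not use this matrix.** The Day 35 ANCOVAs for hemoglobin, ferritin and TSAT, and the observed-case analysis of the primary endpoint, estimate their own Day 35 variance. A reader might infer that the primary p-value is at risk; it is not.
- **The random effect alone does no harm to the estimate.** A reader might infer that pairing it with an unstructured matrix biases the Day 35 result. It does not, because the marginal covariance is the same. The harm needs a convergence failure, and how often that would occur has not been measured. Ten covariance parameters with about 72 participants is not demanding once the redundant term is gone. The phrase may also only identify the subject as the repeated unit, but the SAP does not say so.
- **The direction is not known.** A reader might infer that all four MMRMs would give intervals that are too narrow. The documents contain no early-visit SDs to support that. Ferritin may be most variable soon after dosing, which would make the Day 35 interval too wide. Nothing is quantified for TSAT or CHr.
- **The 8 to 12% range is not the error rate of the full SAP procedure.** It assumes the interaction is kept. With the drop rule the figure is about 7 to 9% under compound symmetry.

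What does not stand is the suggestion that the list is harmless. It contradicts the SAP's own stated aim. If variance components was meant as a separate variance for each visit, the SAP would have to say so, because the standard SAS name does not mean that.

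**Conclusion.** The point holds as a specification defect in supportive analyses and should be corrected before database lock. The redundancy is a matter of algebra: 11 parameters for 10 quantities. That the named fallbacks assume equal variance follows from their standard SAS definitions.

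The consequence is conditional. It requires that a fallback is used and that the Day 35 variance differs from the visit average. For assumed hemoglobin SDs rising to 1.16 g/dL, the Day 35 standard error is about 0.80 to 0.90 of the correct value with the interaction kept (type I error about 8 to 12%). The error is about 7 to 9% under compound symmetry with the drop rule. With equal SDs there is no error, and with falling SDs the interval is too wide. These sizes rest on assumed SDs and correlations, not on trial data.

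Conclusions from the Day 35 ANCOVAs do not change. CHr is the most exposed endpoint, because its section describes no other inferential analysis.

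**What to change.** In SAP 6.1.1, 6.2.1, 6.2.2 and 6.2.6:

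1. Delete the random subject effect and model within-subject correlation through the repeated-measures matrix only.
2. Replace the fallback list with heterogeneous-variance structures in a fixed order, preferring those that do not rely on equal visit spacing: first-order ante-dependence, then heterogeneous compound symmetry. If heterogeneous Toeplitz or heterogeneous AR(1) is added, state the limitation that the gaps are 7, 14 and 7 days.
3. Keep Kenward-Roger with these model-based fits.
4. If an equal-variance structure remains as the last resort, use a sandwich standard error and state its degrees-of-freedom method. A sandwich standard error does not protect the point estimate from a wrong covariance structure when data are missing at random, so it should stay a last resort.
5. Always keep the treatment-by-visit interaction, so that the reported contrast is the Day 35 contrast. Without this, changing the covariance structure alone does not bring the error back to 5% (Step 6).

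The cost is SAP wording in four places and small code changes. Data collection, sample size and the primary analysis are unchanged. The Day 35 interval may be slightly wider.

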#### **8.4.2 Secondary Endpoints**

Secondary efficacy endpoints include:

- Change in ferritin from baseline to Day 35
- Change in TSAT from baseline to Day 35
- Changes from baseline to in hemoglobin, ferritin, TSAT, and reticulocyte hemoglobin content.
- Pharmacokinetic assessments, including  $C_{max}$ ,  $T_{max}$ ,  $AUC_{0-time}$  last measured concentration,  $AUC_{0-infinity}$ ,  $T_{1/2}$ , MRT, Cl,  $V_D$ ,  $V_{Dc}$ ,  $V_{Dss}$ , and  $V_{Darea}$ . These assessments will be

based on a population pharmacokinetic analysis using data from this study and 1VIT13036.

Continuous efficacy endpoints will be analyzed using ANCOVA as described for the primary endpoint. Binary efficacy variables will be analyzed using stratified Cochran-Mantel-Haenszel chi-square tests.

All secondary efficacy endpoints will be analyzed for the mITT population.

Details of analyses for these endpoints will be outlined in the SAP.

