### 2.3.4 Handling of Missing Data

A participant who withdraws from the study for any reason will be included in the analyses regardless of time on study. Methods for handling withdrawals and missing data will be specific to each endpoint to be analyzed. Missing data will not be imputed for descriptive statistical summaries in safety or efficacy.

For statistical inferential (models) analyses, missing data will be imputed using last observation carried forward (LOCF) method for hemoglobin and other efficacy endpoints. e.g. for primary endpoint, hemoglobin, when Day 35 data is missing (subject has discontinued before Day 35, or measurement not taken at Day 35 though subject was not discontinued), Day 28 result will be carried forward. If the post-baseline value of the first scheduled visit is missing, the worst value obtained from the same time point of all subjects in ITT population will be used for both treatment groups. The worst value is defined as the lowest value for hemoglobin, ferritin, TSAT and reticulocyte hemoglobin content.

Supportive analyses will assess the impact of missing values on inferences based on primary efficacy endpoints and missing data will be handled by using missing at random (MAR) in

mixed effect model repeat measurement (MMRM) model. The observed case will also be applied for primary analysis.

Dates missing the day or both day and month of the year will adhere to the following conventions to classify TEAE and to classify prior/concomitant medications.

- A medication with a completely missing start date will be considered a prior medication. A medication with a completely missing stop date will be considered a concomitant medication.
- If complete AE onset date is missing and AE end date is on or after the first dose date then it will be counted as a treatment emergent AE (TEAE) for the study. If complete AE onset date is missing and AE end date is before the first dose date then it will be counted as a not treatment emergent AE (TEAE) for the study.
- If an AE or a medication has a partial missing start or stop date, the following rules will be used for imputation:
  - If year is present but month and day are missing, impute start date as January 1 of that year or first dose date if the year is the same as the year of first dose date and impute stop date as December 31 of that year.

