#### **6.2.6 Change in Reticulocyte Hemoglobin Content from baseline to each visit**

The actual value of reticulocyte hemoglobin content (CHr) on baseline, each post-baseline visit, and change from baseline to each post-baseline visit will be summarized via descriptive statistics by treatment group.

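### All four MMRMs drop treatment-by-visit when it is not significant but still report a Day 35 effect, which the reduced model does not estimate

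*SAP*

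**What the plan says.** The hemoglobin MMRM in SAP 6.1.1 models change at every post-baseline visit, with treatment, visit and treatment-by-visit as fixed effects. Two instructions follow: "If the interaction term is not significant, it will be dropped from the model", and "P-values to test treatment effect on Day 35 will be reported". The same pair appears in the MMRMs for ferritin (6.2.1), TSAT (6.2.2) and CHr (6.2.6). The rule names no significance level, so the general two-sided 0.05 of SAP 2.1 applies.

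The purpose of the hemoglobin model is stated: "To assess the robustness of this primary efficacy analysis, supportive analyses will be performed using the MMRM model". SAP 2.3.4 adds that supportive analyses assess the impact of missing values, and that "The observed case will also be applied for primary analysis". The primary analysis is ANCOVA with LOCF.

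Neither document takes the Day 35 result from the full model after the term has been dropped, or gives the common effect another name.

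**The concern.** The two instructions conflict whenever the interaction is not significant. The number labelled as the Day 35 effect is then the same number the model gives for Day 7: a weighted average over four visits. Failing to reject equality of four visit effects, with about 30 per arm, is not evidence that they are equal. Nor is constancy an obvious default, because FCM is given on Days 0 and 7, oral iron is taken daily for 28 days, and the endpoint is defined at Day 35.

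What is at stake is the robustness check. If the effect builds, the check understates it. If an early effect fades, the check reports it as present at Day 35. Either way, the MMRM can agree or disagree with the ANCOVA for reasons unrelated to missing data, which is what it is meant to examine.

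**Working it through.** **1. The plan's own figure.** The inputs, from SAP 1.3.4, are an "expected difference in hemoglobin of 1.0 g/dL (common standard deviation = 1.16 g/dL"), two-sided 0.05 and 90% power. The normal approximation gives 2 × 1.16² × (1.960 + 1.282)² / 1.0² = 2 × 1.3456 × 10.51 = 28.3, so 29 per arm. The t-based calculation gives 30 per arm (power 90.7%; 89.7% at 29). The stated 60 is reproduced. The plan gives no figure for the MMRM.

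**2. What the reduced model estimates.** In the full model the group difference at visit k is β + γₖ. Dropping the interaction sets every γₖ to zero and leaves β at all visits. With observed visit differences d and covariance matrix S, the estimate is β = 1′S⁻¹d / (1′S⁻¹1), so the visit weights are proportional to S⁻¹1. This is algebra and needs no assumption about the trajectory.

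The size does need assumptions, because the documents give no visit-level effects, SDs or correlations. Take a building effect of 0.2/0.5/0.9/1.0 g/dL at Days 7/14/28/35:

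- *SD 1.16 at every visit, exchangeable correlation.* The weights are 0.25 each, so the common effect is (0.2 + 0.5 + 0.9 + 1.0)/4 = 0.65.
- *SD 0.8/0.95/1.1/1.16, exchangeable correlation 0.5.* With uₖ = 1/SDₖ the weights are proportional to uₖ(uₖ − 0.2Σu). Here u = 1.250, 1.053, 0.909, 0.862 and Σu = 4.074. The products are 0.544, 0.250, 0.086 and 0.041, and the weights 0.591, 0.272, 0.093 and 0.044. The common effect is 0.118 + 0.136 + 0.084 + 0.044 = 0.38. Day 7, where the SD is smallest, dominates.

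**3. The rule as a whole, by simulation.** Four-visit normal changes at weeks 1, 2, 4 and 5; 30 per arm; complete data; no covariates. Correlation is exchangeable 0.5 or 0.7, or serial 0.7 or 0.85 per week. The SD is constant at 1.16 or rises from 0.8 to 1.16 as above. The interaction is tested by a 3-df F at 0.05. If it is not significant the common effect is reported, otherwise the Day 35 contrast.

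| Building effect, true Day 35 value 1.0 | Result |
|---|---|
| Term dropped | about 5-58% of trials |
| Reported effect, mean over all trials | 0.84-0.98 |
| 95% CI covers the true Day 35 effect | 65-93% |
| Significant under the rule | 81-89% |
| Significant if the term is always kept | 90-92% |

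| Building effect, dropped trials only | Constant SD | Rising SD |
|---|---|---|
| Common effect | 0.61-0.68 | 0.20-0.45 |
| Kept-term Day 35 estimate in the same trials | 0.87-0.90 | 0.65-0.83 |

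For a fading effect of 0.3/0.3/0.15/0, with a true Day 35 effect of zero, the rule declares a Day 35 effect in 9-12% of trials (constant SD) or 20-30% (rising SD), against about 5% if the term is kept. For a constant effect of 1.0 there is no bias, and significance is 95-99% under the rule against 90-91% with the term kept.

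**4. Limits.** The simulation omits the strata and baseline covariates, and no SAS model with Kenward-Roger degrees of freedom was fitted. Ferritin, TSAT and CHr were not quantified.

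**The case against.** The strongest reply is that this is a supportive analysis with a small practical effect. Much of that stands. The primary test is the ANCOVA, and ferritin and TSAT have their own ANCOVAs. An observed-case analysis is planned for the primary endpoint, and the by-visit descriptive summaries in SAP 6.2.3 to 6.2.6 would show a changing effect. No decision rule uses an MMRM p-value. If the effect is constant, the rule is unbiased and more precise.

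Three stronger readings are tempting and are not supported:

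- *A reader might set the common effect in dropped trials (0.61-0.68 or 0.20-0.45) against 1.0 and call the gap bias.* Trials in which the term is dropped are selected for a flat observed profile. The kept-term Day 35 estimate in those same trials also falls below 1.0, so part of the gap is selection that the fix would not remove. Over all trials the understatement is 1.0 − 0.98 = 0.02 to 1.0 − 0.84 = 0.16 g/dL.
- *A reader might take 20-30% as the expected false-positive rate.* It requires an early effect that has vanished by Day 35 and SDs that rise over visits. The documents give no specific basis for a fading hemoglobin effect.
- *A reader might say that CHr is left with only an invalid inference.* The CHr endpoint is change throughout the study (SAP 1.2.2), so an effect common to all visits is not foreign to it; only the Day 35 label is wrong. SAP 6.2.6 does describe only descriptive summaries ("The actual value of reticulocyte hemoglobin content (CHr) on baseline, each post-baseline visit, and change from baseline") and this MMRM, whereas protocol 8.4.2 says "Continuous efficacy endpoints will be analyzed using ANCOVA as described for the primary endpoint" and the imputation rule in SAP 2.3.4 names CHr ("The worst value is defined as the lowest value for hemoglobin, ferritin, TSAT and reticulocyte hemoglobin content"). That is a separate discrepancy between the documents and does not follow from the drop rule.

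What the reply does not answer is that the reported quantity changes with a low-powered pretest while its label stays the same.

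**Conclusion.** The point holds as a wrong rule in a supportive analysis, and it should be corrected. That the reduced model has no separate Day 35 effect is certain from the SAP text. Under a building hemoglobin effect the average loss is modest. The clearer damage is to the confidence interval, whose coverage of the true Day 35 effect can fall well below 95%, and to power, which falls below the planned 90%. These sizes rest on the assumed trajectories, correlations and earlier SDs; only the 1.0 g/dL and 1.16 g/dL come from the documents. A reader might infer that the primary efficacy conclusion is compromised. It is not: the primary ANCOVA, its type I error and the sample size do not depend on this rule.

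**What to change.** In the MMRM paragraphs of SAP 6.1.1, 6.2.1, 6.2.2 and 6.2.6:

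- delete the sentence that drops the interaction;
- state that treatment-by-visit is kept whatever its p-value;
- report the Day 35 least-squares mean difference, with its 95% confidence interval and p-value, from that model;
- if a common-effect estimate is also wanted, label it as a weighted average over visits.

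The cost is one sentence in each of four places and a few lines of code. The statistical price is paid only if the effect truly is constant: the Day 35 standard error is then 1.14-1.30 times the pooled one at constant SD, or 1.48-1.61 times with the rising SD. Power at 1.0 g/dL with 30 per arm is then about 90-91% instead of 95-99%, which still meets the planned 90%. No clinical procedure, data collection or primary analysis changes.
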